Following admission to a Pediatric ICU (PICU), critically ill children requiring mechanical ventilation and invasive monitoring receive opioids for analgesia and sedation.^{1, 2} Therapeutic goals for the use of analgesic and sedative drugs are to reduce pain, anxiety, or agitation, allow mechanical ventilation, prevent physiological stress responses and avoid secondary complications.³ PICU patients receive opioid therapy routinely, often leading to opioid tolerance^{4, 5} and dependence.^{6–9} These occur more commonly in infants and children, because of developmental changes in metabolism, excretion or dose/response curves, receptor subtypes, signal transduction, receptor induction, and regulatory pathways. Advances in opioid pharmacology cannot be applied to critically ill children because the incidence and risk factors for opioid tolerance in PICU patients remain unknown. We propose a prospective, observational study of 450 patients to describe the incidence and identify risk factors for opioid tolerance in ventilated children receiving opioid analgesia. The primary endpoint is defined by a doubling of the total daily opioid dose from initiation of opioid therapy; secondary endpoints include alternative measures of opioid tolerance. Data on opioid use, concomitant therapies, demographic and explanatory variables will be collected for the duration of opioid therapy, or 14 days after enrollment, until PICU discharge or the patients death. Rates of opioid tolerance will be summarized as proportions achieving tolerance by 7 and 14 days after initiation of opioids. We will also seek evidence for clinical variables that elevate the risk for opioid tolerance in mechanically ventilated children. Waiver of informed consent will be requested because the studys scientific validity requires 100% accrual of eligible patients.

1 Study Summary

1.1 Hypothesis

The hypothesis of this prospective, observational study is that opioid tolerance occurs frequently in PICU patients, particularly those receiving ≥ 4 days of continuous featanyl or morphine infusions.

1.2 Specific Aims

Specific Aim 1. To describe the incidence of opioid tolerance in ventilated infants and children receiving fentanyl or morphine infusions in the PICU.

Specific Aim 2. To seek evidence of and describe the risk factors associated with development of opioid tolerance in the PICU.

1.3 Primary Endpoint

The primary endpoint for the MOTIF Study is the incidence of opioid tolerance among PICU patients receiving morphine or fentanyl infusions for analgesia and sedation. For the purposes of this study, opioid tolerance is defined by a doubling of the total daily opioid dose from the initiation of opioid therapy (0-24 hours) in the PICU.

1.4 Secondary Endpoints

Secondary endpoints for the MOTIF study are:

- 1. Average daily fentanyl or morphine dose within age groups (μ g/kg/day, all opioid drugs will be normalized to fentanyl equivalent doses using well-established opioid conversion ratios);
- 2. Peak fentanyl or morphine infusion rate (μ g/kg/hour, again all opioid drugs will be normalized to fentanyl equivalent doses using published opioid conversion ratios);
- 3. Total cumulative dose (mg/kg) and duration of fentanyl or morphine exposure (hours) during the stay, measured from the time of the first dose given after PICU admission and until study exit.

1.5 Explanatory Variables

These include demographic and clinical variables (such as age, gender, history of prior exposure, age at first exposure, duration of opioid therapy, use of concomitant medications, etc.) in order to identify possible risk factors for development of opioid tolerance during PICU therapy, and to generate hypotheses for future studies. In addition, since some opioid drugs are highly lipophilic (e.g. fentanyl) and others are not (e.g. morphine), we will calculate BMI and ideal body weight to evaluate the impact of increasing obesity on opioid tolerance.

1.6 Patient Eligibility

1.6.1 Inclusion Criteria

Critically ill children admitted to the PICU are eligible for enrollment if they are:

- between 37 weeks post-conceptional age and less than 18 years; AND
- receiving ventilatory assistance through an endotracheal tube or a tracheostomy; AND
- receiving fentanyl or morphine infusion for analgesia or sedation.

1.6.2 Exclusion Criteria

Children are ineligible to be enrolled as study subjects if ANY of the following is true or anticipated:

- are premature and have not reached the post-conceptional age of 37 weeks, OR
- have a history of drug abuse or alcohol dependence, OR
- for patients less than 3 months old, if the mother has a history of drug abuse during this pregnancy, OR
- are on ECMO or are likely to be placed on ECMO support within 24 hours after PICU admission, OR
- are receiving continuous infusions (of any drugs) for nerve blocks, plexus blocks, or epidural anesthesia, OR
- are receiving opioid therapy via patient-controlled analgesia (PCA) pumps, OR
- were receiving regularly scheduled opioid therapy for more than one week before admission to the PICU, OR
- previously enrolled in this study, OR
- lack of commitment to aggressive intensive care therapies.

1.7 Anticipated Recruitment and Study Duration

We propose enrollment of 450 subjects, a sample size that will permit estimation of the incidence of opioid tolerance with a precision of 4 to 5%. This sample will provide 80% power to detect outcome differences of 14% or higher in exploratory comparisons between subgroups of approximately equal size. The accrual period is anticipated to be between four and 12 months.

1.8 Human Subjects

Waiver of informed consent will be requested for this study because the scientific validity of the study, to determine the true incidence of opioid tolerance among patients admitted to the PICU requires 100% of eligible patients over the study interval. The study fulfills regulatory requirements for a waiver, because there are no changes in clinical practice, no therapeutic interventions, only minimal risk to the patient (loss of privacy), and obtaining informed consent would threaten the scientific validity of the study.

2 Background and Significance

As more and more children survive critical illness and injury, the population of children with special needs is expanding, and the number of children needing pediatric intensive care unit (PICU) admission is concomitantly growing.¹⁰ Advances in monitoring and interventions for hemodynamic instability, airway and ventilator technology, innovative imaging, pediatric general and microsurgical techniques, and the emerging knowledge of the pathophysiology of organ failure are among the developments underlying the remarkable decline in mortality from conditions that were uniformly fatal in the past.^{11–15}

While the decline in mortality and scientific understanding of the pathophysiological basis of pediatric critical care practice are positive developments for children, the consequences of repeated exposure to the environment and interventions of intensive care are of concern to parents, developmental scientists, pediatric generalists and subspecialists,^{16–21} as well as the larger scientific community.^{22–24} Recurrent or prolonged exposure to analgesic and sedation regimens and agents may lead to the induction of drug tolerance and dependence in children with prolonged exposure to these drugs.^{6–9} The unique pharmacology of opioids and other sedative or analgesic agents in infants and children is impacted in a manner that is complex and understudied. The developmental trajectory might be expected to effect changes in metabolism, excretion and dose response curves for these drugs.^{25–28} At critical developmental windows, pediatric patients express unique receptor subtypes (e.g. opioid, glutamate, or serotonin receptors), signal transduction mechanisms, receptor induction, and regulatory pathways that are distinctive from adults.^{29–36}

2.1 Critically Ill Children Routinely Receive Opioid Analgesia

Analgesic regimens for children admitted to the PICU commonly include opioids because of their efficacy in reducing the stress of critical illness, acute pain, postoperative pain, inflammatory pain, and cancer pain.¹ PICU patients receive routine opioid therapy via continuous infusions, potentially facilitating the development of opioid tolerance^{4, 5} and dependence.⁷

In addition to analgesia, sedation is commonly used to alleviate anxiety, agitation, fear, and the risk of accidental extubation, or dislodgement of catheters, drains and monitoring equipment.^{37–42}

The synergy between commonly used analgesic and sedative agents is well known.^{41, 43} There is a paucity of evidence from well-designed randomized controlled trials or prospective cohort studies investigating the safety, efficacy, and clinical utility of analgesic/sedative drugs in pediatric patients.^{44, 45} Investigating the efficacy of analgesia or sedation in critically ill children is also logistically difficult, because of the current lack of validated, sensitive or specific methods for the assessment of analgesia/sedation across all pediatric age groups,^{37, 46–48} different developmental stages, and in children with disability.

2.2 Variability in Current Sedation and Analgesic Strategies in Contemporary PICUs

Surveys of analgesia and sedation practices from PICUs in various developed countries have demonstrated a wide variability in clinical practices.^{39, 40, 42, 44, 49, 50} The use of several drug classes, innumerable agents, huge variation in the doses, frequency, and routes of administration, off-label use of designer drugs approved for adults, various drug combinations or drug rotation regimens occurs routinely^{37, 39–42, 44, 50–53} — often driven by the whims and preferences of individual practitioners. Thus, it is difficult to define best practices, develop guidelines, or to move forward with scientific efforts to elucidate the key questions that might inform practice in this area. Randomized clinical

trials in this population a wait definitive descriptive work that would inform their design. $^{50,\ 51,\ 54}$

Despite these difficulties, consensus guidelines for sedation and analgesia and neuromuscular blockade in PICU patients were recently published using a modified Delphi technique, while highlighting the paucity of highguality evidence and calling for more randomized trials in this area.^{45, 55} A recent prospective study, however, reported considerable variations in clinical practice.⁴⁴ Among the 338 critically ill children studied, 24 sedative and analysic agents were used, more than 30% of ventilated patients received neuromuscular blockade, and 7.4% required physical restraints.⁴⁴ A survey of sedation and analgesia practices in the CPCCRN similarly revealed a huge variability in clinical practice, with the use of many different agents, drug classes, and drug combinations in ventilated and non-ventilated patients (unpublished data, 2007). Observational studies to determine any associations between clinical practices and patient outcomes are necessary for generating hypotheses that can be tested formally. Only after the variables in care have been identified and the outcomes of interest (e.g. opioid tolerance) have been defined would it be possible to proceed with randomized clinical trials.

2.3 Epidemiology of Opioid Tolerance in PICU Patients

Clinical studies of neonates born to heroin-addicted or methadone-maintained mothers were previously extrapolated to the introgenic opioid tolerance caused by prolonged opioid therapy.^{5, 9} Iatrogenic opioid tolerance in young children was first reported from a retrospective chart review in neonates undergoing ECMO,⁵⁶ with 5-fold increases in the fentanyl infusion rate and increases in plasma fentanyl concentrations over 8 days of therapy.^{56, 57} Opioid withdrawal symptoms occurred following a total fentanyl dose of >1.6mg/kg or fentanyl infusions for longer than 5 days.^{56, 57} Subsequent reports^{58–61} suggested that opioid withdrawal occurs in 57% of PICU patients⁷ and in >60% of PICUs, ⁶² despite careful attention to opioid weaning.^{63–65} Increased complications^{66, 67} and prolonged hospital stays occurred among critically ill children with opioid tolerance.^{4, 68} Despite a deeper understanding of the mechanisms underlying opioid tolerance and dependence,⁶⁹ and the availability of novel therapies,^{70–72} none of these advances have been applied to the care of critically ill children. This is mainly because the current prevalence of opioid tolerance in PICU patients remains unknown, and associated risk factors contributing to tolerance in PICU patients have not been described.

2.4 Clinical Significance

Practice variation primarily determined by physician or hospital preference is well described in the management of many medical conditions (e.g., bronchiolitis,^{73, 74} asthma,⁷⁵ transfusion practices,^{76–80} and even determination of brain death⁸¹). Such practice variation, based on physician preferences, is generally associated with poorer clinical outcomes $^{82-85}$ and/or higher costs,^{86–88} and frequently reflects a lack of consensus regarding optimal therapy. As demonstrated by Horn and others,^{73, 87–89} linking the differences in care processes with clinical outcomes is the first step in identifying best practices and thereby improving care. Guidelines to reduce practice variability are associated with improved outcomes, particularly among intensive care patients.^{90–92} The American College of Critical Care Medicine developed guidelines for sedating adult ICU patients in 1995, updated in 2002,^{93, 94} but similar guidelines have not been established for critically ill children. Rampant practice variation occurs in the use of opioid analgesia, often associated with complications, such as opioid tolerance and dependence. Conducting prospective observational studies to clearly define clinical outcomes and measure a baseline incidence of tolerance are important to optimize the use of opioid analgesia for critically ill children.

3 Study Hypothesis and Design

MOTIF is a prospective observational study to determine the incidence and risk factors associated with opioid tolerance in the PICU. All PICU patients treated with opioids are at risk for developing opioid tolerance, although those receiving continuous opioid infusions for ≥ 4 days are at greatest risk. A limited number of exclusions from the study population will ensure the generalization of findings to all ventilated patients in the PICU.

3.1 Hypothesis

The hypothesis of this prospective, observational study is that opioid tolerance occurs frequently in PICU patients, particularly those receiving ≥ 4 days of continuous fentanyl or morphine infusions.

3.2 Specific Aims

Specific Aim 1. To describe the incidence of opioid tolerance in ventilated infants and children receiving fentanyl or morphine infusions in the PICU.

Specific Aim 2. To seek evidence of and describe the risk factors associated with development of opioid tolerance in the PICU.

3.3 Primary Endpoint

The primary endpoint for the MOTIF Study is the incidence of opioid tolerance among PICU patients receiving morphine or fentanyl infusions for analgesia and sedation. For the purposes of this study, opioid tolerance is defined by a doubling of the total daily opioid dose from the initiation of opioid therapy (0-24 hours) in the PICU.

3.4 Secondary Endpoints

Secondary endpoints for the MOTIF study are:

- 1. Average daily fentanyl or morphine dose within age groups (μ g/kg/day, all opioid drugs will be normalized to fentanyl equivalent doses using well-established opioid conversion ratios);
- 2. Peak fentanyl or morphine infusion rate (μ g/kg/hour, again all opioid drugs will be normalized to fentanyl equivalent doses using published opioid conversion ratios);
- 3. Total cumulative dose (mg/kg) and duration of fentanyl or morphine exposure (hours) during the stay, measured from the time of the first dose given after PICU admission and until study exit.

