4.1 Definitions

- **Analgesia:** the reduction or absence of the sense of pain without loss of consciousness, as reported by the patient, or judged clinically from the patients behavior or physiological responses
- **Sedation:** a pharmacologically produced depressed level of consciousness associated with reduced anxiety, stress, and excitement

- First study day: the period from the time that the initial dose of opioid is received in the PICU up to 23:59 hours on that day
- **Subsequent study days:** each calendar day starting at midnight (00:00 hours) and ending at 23:59 hours after the completion of the first study day (as defined above) during which the enrolled subject is an inpatient in the PICU
- **Ventilated day:** PICU day during any part of which the child requires mechanical ventilation support greater than chronic baseline requirements (out of the hospital), provided by endotracheal tube, tracheostomy, laryngeal or face mask
- **Invasive procedure:** Any procedure that breaks the skin barrier or mucous membrane barrier or involves the placement of a medical device (catheter, probe, electrode, drain, prosthetic, or anything else) into a body orifice or body cavity, other than momentary suctioning of the nose, mouth, endotracheal tube, or tracheostomy tube.
- **Opioid tolerance:** the need for increasing doses of opioid drugs in order to maintain the same pharmacological effects as those seen at the initiation of therapy. For the purposes of this study, opioid tolerance is clinically defined as a doubling of the total daily opioid dose (including infusions and boluses) as compared to the total daily opioid dose required during the first 24 hours of opioid therapy, in order to maintain adequate analgesia and sedation
- **Regularly scheduled opioids:** the subject receives opioid drugs daily, given at regularly scheduled intervals. In response to specific symptoms or signs, if the subject has received more than one opioid dose per day, on more than three days during the past week, or a total of more than six opioid doses in the past one week, then they will be considered equivalent to those receiving regularly scheduled opioids.
- **Chronic opioid treatment:** if the subject has received scheduled regular opioids (as defined above) for more than one week, they will be classified as receiving chronic opioid treatment.

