4.3 Subsequent Daily Data Elements

Study Day One is the day of enrollment, beginning at the time of the first morphine or fentanyl administration in the PICU, and ending at 23:59 on that day. Each subsequent study day is defined as midnight (00:00) to 23:59. On each subsequent day (not study day one), the following data elements

Sedative Drugs and Components Sedative Drugs Answer Ketamine Yes or No Propofol Yes or No Chloral hydrate Yes or No Chlorpheniramine Yes or No Clonazepam Yes or No Diazepam Yes or No Droperidol Yes or No Etomidate Yes or No Yes or No Haloperidol Yes or No Hydroxyzine Methohexital Yes or No Yes or No Pentobarbital Phenobarbital Yes or No Promethazine Yes or No Yes or No Thiopental Yes or No Other (specify)

Table 1: Sedative agents.

Analgesic Drugs and	Components
Analgesic Drugs	Answer
Dexmedetomidine	Yes or No
Acetaminophen	Yes or No
Ibuprofen	Yes or No
Acetylsalicylic acid	Yes or No
Alfentanil	Yes or No
Buprenorphine	Yes or No
Butorphanol	Yes or No
Clonidine	Yes or No
Codeine	Yes or No
Dextromethorphan	Yes or No
Hydromorphone	Yes or No
Ketorolac	Yes or No
Meperidine	Yes or No
Methadone	Yes or No
Nalbuphine	Yes or No
Oxymorphone	Yes or No
Remifentanil	Yes or No
Tramadol	Yes or No
Other (specify)	Yes or No

Analgesic Drugs and Components

Table 2: Analgesic agents.

will be collected. This daily data collection will continue through Study Day 14, discontinuation of opioid therapy, death, or PICU discharge, whichever occurs earliest.

- 1. Date of data collection
- 2. Study day number (2 to 14)
- 3. Weight (kg) last measured or estimated weight
- 4. Was morphine or fentanyl infusion weaned (decreased) in the past 24 hours? (Yes or No)
- Was morphine or fentanyl infusion discontinued in the past 24 hours? (Yes or No) If yes to this question,
 - (a) Was morphine or fentanyl infusion restarted in the past 24 hours? (Yes or No)
 - (b) Were intermittent opioid doses started in the past 24 hours? (Yes or No)
- 6. Were muscle relaxants used in the past 24 hours? (Yes or No)
- 7. Were physical restraints used in the past 24 hours? (Yes or No)
- 8. Did inadvertent or unplanned dislodgement of an endotracheal tube occur in the past 24 hours? (Yes or No)
- 9. Did inadvertent or unplanned dislodgement of a central venous line occur in the past 24 hours? (Yes or No)
- 10. Did inadvertent or unplanned dislodgement of an arterial line occur in the past 24 hours? (Yes or No)

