- 11. Did inadvertent or unplanned dislodgement of a thoracostomy tube occur in the past 24 hours? (Yes or No)
- 12. Did inadvertent or unplanned dislodgement of a peripheral venous line occur in the past 24 hours? (Yes or No)
- 13. Did inadvertent or unplanned dislodgement of a surgical drain occur in the past 24 hours? (Yes or No)

- 14. Did inadvertent or unplanned dislodgement of a urinary catheter occur in the past 24 hours? (Yes or No)
- 15. Total amount of morphine or fentanyl (mg/kg) given on this study day (total amounts of drug infusion plus additional boluses, from 00:00 to 23:59 hours)
- 16. Peak hourly dose of fentanyl or morphine given during the 24 hour day $(\mu g/kg/hr)$
- 17. If the subject is receiving midazolam by continuous IV infusion,
 - Number of hours that the midazolam drip was continued in the 24 hour day
 - Highest hourly dose (mg/kg) for midazolam given during the 24 hour day
- 18. If the subject is receiving intermittent lorazepam (by any route), total dose (mg/kg) given during the 24 hour day
- 19. Identify all other sedative (Table 1 on page 22) or analgesic (Table 2 on page 23) agents used during the first study day. If drug combinations are used, record all components of the drug combination.
- 20. Did the subject undergo a surgical procedure during this 24 hour period? Yes or no
- 21. If the subject did undergo a surgical procedure, select the category:
 - Cardiac surgery
 - Neurosurgery
 - Transplant surgery
 - Trauma surgery
 - Other surgery
- 22. Did the subject undergo any invasive procedures during this 24 hour period? Yes or no
- 23. If yes, how many procedures?
- 24. Did the subject have a creatinine > 1.2 during this 24 hour period? Yes or no

- 25. If yes, is the patient requiring dialysis or continuous renal replacement therapy? Yes or no
- 26. Did the subject have hepatic dysfunction associated with an INR > 2.0 during this 24 hour period? Yes or no

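### Dose is collected only for morphine or fentanyl, so neither the total daily opioid dose nor the all-opioid normalization can be computed for a child given another opioid

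*Protocol*

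**What the plan says.** **Primary endpoint.** Protocol 3.3 (also 1.3 and 5.1) states that "opioid tolerance is defined by a doubling of the total daily opioid dose from the initiation of opioid therapy (0-24 hours) in the PICU". The working definition in 4.1 reads "a doubling of the total daily opioid dose (including infusions and boluses) as compared to the total daily opioid dose required during the first 24", the unit being hours. Neither text limits the total to two drugs, and neither mentions conversion between opioids.

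**Secondary endpoints.** For endpoint 1, section 3.4 says "all opioid drugs will be normalized to fentanyl equivalent doses using well-established opioid conversion ratios". Endpoint 2 carries a parallel promise. No ratio is listed. Endpoint 3 is "Total cumulative dose (mg/kg) and duration of fentanyl or morphine exposure (hours) during the stay", with no conversion stated.

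**Dose data.** Item 15 of 4.3 collects "Total amount of morphine or fentanyl (mg/kg) given on this study day". Item 21 of 4.2 does the same for day one, and item 16 of 4.3 takes one peak hourly value for either drug. No listed element says which drug the figure belongs to.

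**Other opioids.** These appear in "Table 2: Analgesic agents", where every agent is answered Yes or No. Item 5(b) of 4.3, on intermittent opioid doses, is also Yes/No.

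**Follow-up and amendments.** Sections 4 and 4.3 continue daily collection until opioid therapy ends, day 14, death or PICU discharge. Section 5.1 keeps children who die or are discharged in the denominator, and no rule removes a child who changes opioid. Section 4 requires a protocol amendment to add a data element; only choice sets may change without one.

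**The concern.** Two stated quantities, the all-opioid daily total and its fentanyl-equivalent form, need doses that the data list does not contain. A child moved from fentanyl to, say, methadone or hydromorphone is still on opioid therapy and still observed, but the recorded morphine-or-fentanyl dose falls towards zero. If that child's opioid requirement later doubles, the data cannot show it.

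The second route to error lies within the two recorded drugs. If morphine and fentanyl milligrams were compared without conversion, a change of drug alone could cross the doubling threshold or mask a true doubling.

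The protocol foresees such changes. Section 2.2 describes drug rotation as routine, and the exit form in 4.4 asks about methadone and buprenorphine at PICU discharge. At stake are the incidence estimate (Aim 1), the classification of individual children in the risk-factor models (Aim 2), and the design figures that 5.4 intends to pass to a later trial.

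**Working it through.** **1. The plan's own precision.** Inputs from 5.4: N = 450, 95% confidence, outcome rate at least 25%. Half-width = 1.96 × √(p(1−p)/450).
- p = 0.25: 1.96 × √(0.1875/450) = 4.00 points
- p = 0.35: 4.41 points
- p = 0.50: 4.62 points

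The stated 4-5% reproduces. It is the yardstick for what follows.

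**2. What can be computed.** Table 2 contains eleven opioids with no dose element: alfentanil, buprenorphine, butorphanol, codeine, hydromorphone, meperidine, methadone, nalbuphine, oxymorphone, remifentanil and tramadol (dextromethorphan not counted). For a child given any of these, the all-opioid daily total and its fentanyl equivalent cannot be calculated, whatever ratios are later adopted.

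**3. Effect of an unconverted switch.** Let g be the true equianalgesic dose ratio to day one and R the morphine-to-fentanyl milligram ratio. R is not in the documents; it is assumed to lie between 10 and 100.
- Fentanyl to morphine: recorded ratio = g × R. With g = 1 (no true change) it is 10 to 100, above the threshold of 2.
- Morphine to fentanyl: recorded ratio = g / R. With g = 2 to 5 (true tolerance) it is 2/100 = 0.02 to 5/10 = 0.5, below the threshold.
- To an opioid without a recorded dose: if all morphine and fentanyl stop, the recorded ratio is 0; if half the day-one dose continues, it is 0.5, even when the true total has doubled.

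**4. Bias in incidence.** Let p be true incidence, s the share switched before any doubling, and f the share of switches going fentanyl to morphine. The other switches go to fentanyl or to an opioid without a recorded dose. Assume switchers have the same true incidence as other children. Then observed incidence = p(1−s) + s·f, and bias = s(f − p).

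| p = 0.25 | s = 5% (22.5 children) | s = 10% (45 children) |
|---|---|---|
| f = 1 | 0.05 × 0.75 = +3.75 points | +7.5 points |
| f = 0.5 | 0.05 × 0.25 = +1.25 points | +2.5 points |
| f = 0 | 0.05 × (−0.25) = −1.25 points | −2.5 points |

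The share of switchers misclassified is 75%, 50% and 25% respectively. In the middle row the net bias is small because errors partly cancel, but 11 (s = 5%) or 22.5 (s = 10%) children still carry the wrong outcome into the regression models.

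At p = 0.50, f = 1 and f = 0 give ±2.5 points (s = 5%) and ±5 points (s = 10%).

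**5. Break-even.** At p = 0.25 with all switches fentanyl to morphine, bias equals 4 points at s = 4/0.75 = 5.3% and 5 points at s = 5/0.75 = 6.7%. With f = 0, a bias of −4 points needs s = 4/0.25 = 16%.

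**The case against.** The best defence is a narrower reading. The aims, eligibility and endpoint wording centre on fentanyl or morphine, the definition's infusions and boluses match the morphine-or-fentanyl dose items, and the Table 2 agents can serve as concomitant drugs in the risk-factor analysis. On that reading only the phrase about all opioid drugs is loose. The reading is coherent, but the protocol does not state it. The endpoint text and the normalization promise both say otherwise, so the passages must be reconciled.

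Several stronger inferences are tempting and should not be drawn.
- *Every switch is misclassified.* It is not. A child who doubled beforehand is already counted. A truly tolerant child moved from fentanyl to morphine is still called tolerant. A child who never doubles and moves to fentanyl or to an unrecorded opioid is still called non-tolerant.
- *With 5-20% switched, the error is 5-20 points.* That is a ceiling, with every switcher wrong in the same direction. The formula gives +3.75 to +15 or −1.25 to −5 at p = 0.25. The rate itself is assumed: section 2.2 speaks of rotation across drug classes and gives no frequency of opioid switching.
- *Raw milligrams of the two drugs are summed.* The list does not prove this. The electronic form may hold separate fields, and secondary endpoints 1 and 2 presuppose that the drug is known. Extending conversion to the primary endpoint and listing ratios could be done in an analysis plan.
- *Changing weight invalidates the ratio.* Item 3 of 4.3 takes "Weight (kg) last measured or estimated weight" daily, and weight is also recorded at entry. Absolute dose is therefore recoverable if the recorded weight was the divisor. This is minor.

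None of these concessions recovers the doses of the eleven other opioids. An analysis plan cannot supply data that were not collected.

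**Conclusion.** The point stands as an internal contradiction: the protocol defines an all-opioid endpoint and promises an all-opioid normalization that its own data list cannot support for children given any of eleven opioids. That part needs no assumption. The lack of a stated conversion for the primary endpoint and secondary endpoint 3, and of an element naming the drug, is a weaker gap, because the form and the analysis plan could close it.

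The numerical effect is conditional. With 25% true incidence, 5-10% of children switched before doubling, switchers no different in true incidence, and no conversion, bias lies between −2.5 and +7.5 points, depending on the direction of switching. Even with full conversion of morphine and fentanyl, switches to an opioid without a recorded dose would leave the downward component: −1.25 to −2.5 points if all switches were of that kind. Set against a 4-5 point precision, this should be settled before enrolment.

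**What to change.** **Preferred.** In 4.2 and 4.3, record daily dose separately for morphine, fentanyl and any other systemic opioid given. State once that conversion to fentanyl equivalents applies to the primary endpoint and to all dose-based secondary endpoints.

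**If the other doses will not be collected.** Restrict the primary endpoint and the normalization wording in 3.3, 3.4, 4.1, 5.1 and 5.2 (and the matching summary sections) explicitly to morphine plus fentanyl in fentanyl equivalents. Add two sensitivity analyses: one censoring at first use of another opioid, using a time-to-event estimate of the 7- and 14-day incidence, and one counting such switches as events.

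**In either case.** Correct item 19 of 4.3: it sits in the daily list for later days but asks about agents used on the first study day, so even the Yes/No record of later opioid use is uncertain as worded.

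**Cost.** A protocol amendment and a few extra dose fields from the same medication chart. The form could hold up to eleven more drugs over as many as 14 days, but entries are needed only for opioids actually given. The sample size of 450 and the planned precision do not change.
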